3. RESEARCH FUNDING

The only research to be conducted specifically for this study is the BIA analysis. This will be carried out by the researcher using equipment belonging to the University of Tartu (UT), for which no additional fee will be charged. The equipment used includes a bioelectrical impedance analysis device, which is already available and in use in the nephrology department. All other reviewed tests are those that have already been performed for clinical reasons and registered in the patients' hospital records in the eHL system.

The study (comparative analysis of bioelectrical impedance analysis (BIA) and estimated glomerular filtration rate (eGFR) for assessing nutritional status in hemodialysis patients) does not have an external funding source. This study will be conducted in compliance with ethical research standards. All aspects of the study, including data collection, analysis, and reporting, will be carried out without external financial support.

4. BRIEF OVERVIEW OF PREVIOUS RESEARCH ON THE SAME TOPIC

A critical review highlights how BIA helps measure body composition and hydration, particularly intracellular and extracellular water, in patients with chronic kidney disease (CKD) and heart failure. It emphasizes the potential of BIA in managing fluid overload but notes that standardization and further validation are needed for routine clinical use (1). A 2024 study presented at the ASN Kidney Week identified BIA markers, such as phase angle and hydration indices, as potential predictors of CKD progression. These findings suggest that BIA is a valuable tool for non-invasive monitoring alongside traditional methods like eGFR (2).

BIA and eGFR have complementary roles in managing the nutritional and hydration status of CKD patients. The integration of both tools allows for better monitoring and the application of individualized treatment plans, improving clinical outcomes (3).

The value of integrating bioelectrical impedance analysis (BIA) and estimated glomerular filtration rate (eGFR) in the treatment of CKD has been recognized. BIA provides detailed information on body composition, such as fat mass, fat-free mass, and hydration levels, enabling better nutritional and fluid management, particularly in patients with malnutrition or fluid overload. BIA-derived metrics, including phase angle and extracellular fluid volume, have proven useful in assessing CKD progression and dialysis adequacy, complementing eGFR in evaluating the patient's overall health status (2) (3).

5. OBJECTIVE, SUMMARY, AND RATIONALE OF THE PROPOSED RESEARCH

The primary objective of the study is to assess the correlation between BIA-derived body composition parameters (e.g., fat mass, fat-free mass, total body water, phase angle) and eGFR in hemodialysis patients.

The study will investigate how BIA and eGFR can be used together to more effectively monitor nutritional interventions in hemodialysis patients. The study will also assess the prevalence of malnutrition and protein-energy wasting (PEW) in the study population using BIA and eGFR data.

Hemodialysis patients often suffer from complex nutritional problems due to the interplay between kidney function, protein-energy wasting, and fluid management. Current nutritional assessments in hemodialysis patients are limited, with most relying on clinical observations or basic biochemical tests. A more comprehensive, non-invasive approach is needed to assess both nutritional status and fluid balance. The study will determine whether comparing BIA metrics with eGFR provides a better picture of the patient's nutritional and kidney health, which could improve patient outcomes and dialysis management.

Malnutrition, fluid balance disorders, and protein-energy wasting (PEW) are common in hemodialysis patients due to the effects of chronic kidney disease (CKD) and dialysis therapy. Nutritional status is a critical factor influencing patient outcomes but is often under-monitored.

Traditional methods of assessing kidney function, such as estimated glomerular filtration rate (eGFR), provide an overview of kidney health but do not directly measure body composition or nutritional value. In contrast, bioelectrical impedance analysis (BIA) provides detailed information on body composition, including fat mass, fat-free mass, total body water, and phase angle. The aim

of this study is to investigate the relationship between BIA-derived nutritional markers and eGFR to assess their combined utility in evaluating the nutritional status of hemodialysis patients.

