7. INCLUSION AND EXCLUSION CRITERIA

Sample size: 25-30 adult hemodialysis patients will be recruited.

Inclusion criteria:

- Patients must be 18 years or older.
- Patients must have been receiving regular hemodialysis for at least the last 6 months.

Exclusion criteria:

- Patients with a pacemaker or implanted defibrillator will not be included, as these are contraindications for BIA.
- Pregnant women will not be included due to changes in body composition and safety concerns.
- Patients who have recently had an acute illness or surgery that affected their hydration or nutritional status, as this could provide inaccurate body composition results.

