8. RESEARCH METHODOLOGY DESCRIPTION

Study type: Observational, cross-sectional study

Data collection:

Patient data will be collected from the hemodialysis department of Tartu University Hospital. All participating patients will undergo BIA. BIA analysis will be performed using dialysis-related measurement instruments, as described in the methodology section. This will be done before routine dialysis and does not require a separate visit. The patient does not need to come in specifically for this purpose.

The following data will be collected from participating patients:

Demographic data:

- Age
- Gender
- Height
- Weight
- Body mass index (BMI)
- Duration of dialysis (months/years)

Bioelectrical impedance analysis (BIA):

- Fat mass
- Fat-free mass

- Total body water
- Extracellular water
- Phase angle

Laboratory parameters:

- eGFR

Bioelectrical impedance measures body fat, muscle, and water using a low-voltage electric current that is harmless and imperceptible to the patient. Two electrodes are placed on the wrist and two on the ankle, similar to an EKG but faster (approximately 5 minutes). Although the procedure is safe, it requires minimal patient preparation. Measurements will only be taken from patients who consent. Measurements include fat mass, fat-free mass, total body water, extracellular water, and phase angle. To minimize fluid shifts, measurements will be taken before dialysis. eGFR will be taken from the patient's recent blood test. eGFR data will be collected routinely and will use measurements from the last 6 months. Clinical data such as dialysis duration and comorbidities will also be considered.

Data analysis will be performed using statistical software (SPSS).

The analysis will include several steps to thoroughly evaluate the relationship between bioelectrical impedance analysis (BIA) parameters and estimated glomerular filtration rate (eGFR) in hemodialysis patients. Descriptive statistics will summarize the main characteristics, such as age, gender, dialysis duration, eGFR, and BIA parameters. Pearson or Spearman correlation tests will be used to assess relationships between BIA measurements (e.g., fat mass, lean body mass, phase angle) and eGFR. Multivariate regression analysis will identify significant predictors of malnutrition and clinical outcomes, focusing on factors such as phase angle, lean body mass, and fluid status.

Data will be collected from the hemodialysis department of Tartu University Hospital.

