11. PREVIOUS OR SIMULTANEOUS EVALUATIONS OR APPROVALS OF THE SAME PROJECT ELSEWHERE

The integration of bioelectrical impedance analysis (BIA) and estimated glomerular filtration rate (eGFR) for assessing nutritional status in hemodialysis patients is an active area of research. Although several studies have explored the use of BIA for assessing body composition and nutritional health in this patient population, the integration of BIA with eGFR for this specific

purpose remains an emerging field. Further studies are needed to validate combined assessment models and establish standardized protocols for their use in clinical practice.

A comprehensive review highlighted the use of BIA in managing the nutrition of CKD patients, including those on hemodialysis. The review emphasized the role of BIA in measuring body composition parameters such as fat-free mass, fat mass, phase angle, and body water, which are crucial for assessing nutritional status and guiding interventions (4).

Another study examined changes in body composition during the transition to hemodialysis using BIA to assess nutritional value (phase angle) and hydration (vector length). The findings showed that starting dialysis is associated with changes in body composition, reflecting changes in cellular integrity and fluid volume control (5).

Another study investigated the performance of BIA and anthropometric measurements in assessing body composition in CKD patients in stages 3–5, including those on dialysis. The study found that BIA can assess body composition across different stages of CKD, with eGFR calculated using the CKD-EPI equation. This highlights the potential of combining BIA and eGFR for monitoring nutritional status and disease progression (6).

Direct studies linking BIA and eGFR for assessing nutritional status in hemodialysis patients are limited, but existing studies suggest that both metrics are valuable. Their combined application allows for a more comprehensive assessment of patient health, warranting further research in this area.

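### If the laboratory eGFR is creatinine-based, muscle enters both sides of the primary correlation for the lean BIA measures, so those correlations cannot be read as evidence about kidney function

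*Protocol*

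**What the plan says.** - **Objective (Protocol section 5):** "The primary objective of the study is to assess the correlation between BIA-derived body composition parameters" and eGFR. The parameters named are fat mass, fat-free mass, total body water and phase angle. The section describes eGFR as an overview of kidney health that does not directly measure body composition, and aims to judge how useful the two are together.
- **Population (section 7):** "Patients must have been receiving regular hemodialysis for at least the last 6 months". "Sample size: 25-30 adult hemodialysis patients will be recruited".
- **Source of eGFR (section 8):** "eGFR will be taken from the patient's recent blood test", and "eGFR data will be collected routinely and will use measurements from the last 6 months". It is the only laboratory parameter listed. The marker (creatinine or cystatin C) and the equation are not given. CKD-EPI appears only in section 11, in the account of a cited study.
- **Analysis (section 8):** "Pearson or Spearman correlation tests will be used to assess relationships between BIA measurements (e.g., fat mass, lean body mass, phase angle) and eGFR". No adjustment is mentioned for these correlations.
- **Use of the two together (section 11):** "Their combined application allows for a more comprehensive assessment of patient health".

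The protocol nowhere says that an eGFR value may itself depend on muscle.

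**The concern.** The plan treats eGFR and the BIA lean measures as two separate sources of information, to be correlated and then combined. If eGFR is creatinine-based, they are not separate. Creatinine is produced by muscle, and fat-free mass measures largely that tissue. Between two patients of the same age, sex and clearance, the more muscular one has the higher creatinine and so the lower eGFR. In patients on long-term hemodialysis, differences in kidney clearance may drive creatinine less, and muscle more, than in patients not on dialysis.

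What is at stake is the meaning of the primary result. A null or negative correlation of eGFR with fat-free mass could be reported as a finding about kidney function when part or all of it is creatinine generation. A positive one would be distorted too. In neither case could it serve as independent support for using BIA and eGFR together.

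**Working it through.** **What the documents supply.** They give the two sides of the correlation, the population, n = 25-30 and the type of test. They give no expected correlation, power or alpha, so there is no plan figure to reproduce. Every other input below is an assumption.

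**1. Direction.** Let M be muscle (fat-free mass), K total creatinine clearance and C serum creatinine, with C = M^g / K × error and eGFR proportional to C^(-b), b > 0, within one age and sex group. Let sM, sK and sE be the log-scale SDs of M, K and the error, and rho the true correlation of ln M with ln K. Then

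corr(ln M, ln eGFR) = (rho·sK - g·sM) / sqrt(sK² + g²·sM² - 2·g·rho·sM·sK + sE²).

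The term -g·sM can only lower the numerator. The sign is negative when rho < g·sM/sK. The exponent b cancels, so the result does not depend on the exponent of the equation.

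**2. Example (sM 0.15, sK 0.30, sE 0.10).**
- g = 1, rho = 0: -0.15 / sqrt(0.09 + 0.0225 + 0.01) = -0.15 / 0.35 = -0.43.
- g = 1, rho = 0.5: numerator 0.15 - 0.15 = 0, so a true 0.5 is seen as 0.00.
- g = 0.5, rho = 0: -0.075 / 0.325 = -0.23.
- g = 0.5, rho = 0.5: 0.075 / 0.288 = +0.26, attenuated but not reversed.

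**3. Range (sM 0.10-0.20, sK 0.10-0.50, sE 0.10, g 0.5-1).**

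| True rho | Expected correlation with eGFR |
|---|---|
| 0 | -0.10 to -0.82 |
| 0.3 | -0.78 to +0.20 |
| 0.5 | -0.75 to +0.41 |

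Every cell lies below the true value. The most negative values need clearance to vary much less than muscle (sK 0.10, sM 0.20).

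**4. With an equation that has age and sex terms.** Large simulations used creatinine exponent -1.2, generation power 0.5-1 and differing assumed body-composition inputs. With no true relation, the age- and sex-adjusted correlation was -0.17 to -0.57, -0.16 to -0.52 and -0.11 to -0.42 in three sets of runs, hence about -0.1 to -0.6. Unadjusted, as the protocol plans, it ran from -0.43 to about +0.05. The equation's age and sex terms work against the muscle effect there.

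With a true positive relation and dialysis clearance in the creatinine balance, the adjusted results were:
- generation power 1, true r 0.32 to 0.71: observed -0.17 to -0.29 (reversed);
- generation power 0.5, true r 0.33 and 0.67: observed -0.03 and +0.17 (hidden or attenuated).

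A further set at power 0.5 gave -0.05 to +0.44 for true r 0.28 to 0.58.

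**5. At the planned sample size.** Spearman, 4,000 replicates, n = 25 and 30, g = 1 (the strong end), sM 0.15, error log-SD 0.10, residual GFR median 4 mL/min with log-SD 0.5, no age or sex terms. Here rho is the correlation with residual GFR. Ranges run from n = 25 to n = 30.

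| True rho | Dialysis clearance (mL/min) | Mean observed | Significantly negative | Significantly positive | Significantly positive using true residual GFR |
|---|---|---|---|---|---|
| 0 | 0 | -0.26 | 26-29% | 0% | 2-3% |
| 0 | 10 | -0.58 | 88-94% | 0% | 3% |
| 0.3 | 0 | 0.00 | 2-3% | 2-3% | 27-34% |
| 0.3 | 10 | -0.46 | 67-75% | 0% | 28-34% |
| 0.5 | 0 | +0.20 to +0.21 | 0% | 16-21% | 68-78% |
| 0.5 | 10 | -0.37 | 46-54% | 0% | 68-78% |

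For scale, the critical |r| at two-sided 0.05 is t / sqrt(n - 2 + t²): 0.40 at n = 25 and 0.36 at n = 30. For 80% power, tanh((1.96 + 0.84) / sqrt(n - 3)) gives 0.54 and 0.49. The artefact can be as large as any effect this study could detect.

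**6. Would serum creatinine separate artefact from a real relation?** Given age and sex, ln eGFR = constant - b·ln C. The adjusted creatinine correlation is therefore the eGFR correlation with its sign changed. In simulation, artefact alone gave -0.49 with eGFR and +0.50 with creatinine. A genuine negative relation (true r -0.48) with no muscle-creatinine link gave -0.44 and about +0.44. The two patterns look the same.

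**The case against.** **The premise is unconfirmed.** The protocol does not say the eGFR is creatinine-based; with a cystatin C-based value the argument would largely fall away. This stands, and is why the point is conditional and the fix begins with naming the marker.

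**The size is not known.** No exponent, spread, generation power or clearance comes from the documents. A reader might infer that the sign of a true positive relation will be reversed. The documents do not support that. Reversal needs creatinine generation to scale strongly with muscle and dialysis to dominate clearance. With weaker scaling the result is often near zero or still positive. The planned correlation is also unadjusted, and its shift can be close to nil.

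**The scope is limited.** Fat mass is also a primary parameter and is not affected in the same way. Only fat-free mass was modelled; total body water and phase angle follow by extension. This stands.

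**The harm is inferred.** The aim is descriptive, and section 9 promises transparency about limitations; interpretation could be left to the report. This stands only in part. Section 5 presents eGFR as a kidney measure and sets out to judge its joint use with BIA, so the plan as written would report a muscle-contaminated correlation as evidence on both.

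**A tempting check does not work.** A reader might infer that a negative eGFR correlation beside a positive creatinine correlation proves creatinine generation. It does not, because the second only mirrors the first once age and sex are adjusted for.

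**Conclusion.** The point holds conditionally. If the laboratory eGFR is creatinine-based, the lean-measure part of the primary objective correlates muscle with a quantity that falls as muscle rises. The adjusted fat-free mass correlation is then shifted downwards in every scenario with a muscle-creatinine link: about -0.1 to -0.6 with no true relation in the simulations that included age and sex terms, with attenuation, masking or possibly reversal of a true positive relation. The direction follows from the mechanism. The size rests wholly on assumed inputs, and the planned unadjusted correlation may be shifted less. The defect lies in the choice of primary variables and the conclusion to be drawn from them, and a later analysis plan cannot remove it by adjusting for age and sex. It should be corrected before the results are interpreted, with medium confidence because the marker is not stated.

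**What to change.** 1. **Section 8:** state which marker and which equation produce the eGFR.
2. **Section 5:** state that, if the eGFR is creatinine-based, its correlations with fat-free mass, total body water and phase angle will be reported as descriptive and confounded by creatinine generation, whatever their sign. They will not be presented as evidence about kidney function or as independent support for combining BIA with eGFR.
3. **Section 8, if available:** where the hospital record already holds a muscle-independent measure of kidney function, add it to the data list and report its correlation with the same BIA parameters alongside.
4. Do not adopt a rule that uses serum creatinine to attribute a negative eGFR correlation to creatinine generation; it would also label a genuine relation an artefact.

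**Cost:** a few lines of protocol text and, for item 3, one value from existing records. No new test or visit is needed. The downside is a narrower conclusion from the lean-measure correlations; fat mass is not restricted by this point.

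### Malnutrition is to be classified from BIA and eGFR, and its predictors are then sought among outputs of the same BIA measurement, so the non-primary malnutrition regression is, on its face, fully or partly circular

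*Protocol*

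**What the plan says.** Section 5 names the correlation of BIA parameters with eGFR as the primary objective. It then adds a prevalence aim and its data source: "The study will also assess the prevalence of malnutrition and protein-energy wasting (PEW) in the study population using BIA and eGFR data". The same section says that traditional kidney-function measures such as eGFR "do not directly measure body composition or nutritional value".

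Section 8 describes the regression: "Multivariate regression analysis will identify significant predictors of malnutrition and clinical outcomes", "focusing on factors such as phase angle, lean body mass, and fluid status". It lists the BIA outputs: "Measurements include fat mass, fat-free mass, total body water, extracellular water, and phase angle". The only laboratory parameter listed is eGFR. BMI is collected with the demographic data, and "Clinical data such as dialysis duration and comorbidities will also be considered".

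Section 3 states: "The only research to be conducted specifically for this study is the BIA analysis". All other tests come from existing hospital records. Section 7 gives the size: "Sample size: 25-30 adult hemodialysis patients will be recruited".

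**The concern.** A regression for predictors of malnutrition is informative when the outcome is established separately from the predictors. Here the only stated source of the malnutrition classification is BIA together with eGFR. Since the protocol itself says that eGFR does not measure nutrition directly, the nutritional content must come mainly from BIA. The predictors in focus are BIA outputs too: phase angle directly, lean body mass as fat-free mass, and fluid status through total body and extracellular water.

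The harm is to interpretation. A significant BIA predictor of a BIA-based label mainly shows that BIA outputs from one measurement correlate with each other. Reported as a predictor of malnutrition, it would be read as support for BIA as a nutritional tool, which is the question the study wants to inform.

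**Working it through.** The protocol gives no figure to reproduce: no malnutrition definition, prevalence, correlation among BIA outputs or significance level. The check is therefore structural, followed by an illustration under stated assumptions.

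**Step 1: the two sides of the regression.**

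| | Stated source | Protocol section |
|---|---|---|
| Outcome (malnutrition/PEW) | BIA and eGFR data | 5 |
| Predictors in focus | phase angle, lean body mass, fluid status | 8 |
| Origin of those predictors | the BIA measurement taken before dialysis | 8 |
| Other data collected | demographics with BMI, eGFR, dialysis duration, comorbidities | 8 |
| Nutritional reference independent of BIA and eGFR | none named | - |

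The link between the first two rows is an inference: Section 8 does not define its outcome. It is the only reading for which the protocol supplies a basis.

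**Step 2: full overlap.** Suppose malnutrition is a cut-off on one BIA variable and that variable is also a predictor. It then sorts cases from non-cases without error. A logistic model shows complete separation in every data set, so no finite maximum-likelihood estimate exists. This follows by definition, whatever the sample size.

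**Step 3: partial overlap.** Assumptions, none of them from the protocol: BIA outputs are standard normal with common correlation r = 0.3, 0.5 or 0.7; malnutrition is the lowest 20% or 40% of one output; two-sided 5% level. The sample size of 25-30 is from Section 7. eGFR is left out of the simulated classification for simplicity. Cases: 0.20 × 25 = 5 to 0.40 × 30 = 12.

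*One different BIA output tested alone* (two-group t-test), share of studies with p<0.05:
- r = 0.3: 16-26%
- r = 0.5: 40-62%
- r = 0.7: 74-94%
- r = 0: about 5%

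*Three different BIA outputs entered jointly* (linear model, outcome cut on a fourth output), which is closer to the multivariable model of Section 8, over r = 0.3-0.7:
- a given predictor: about 8-16%, against 5% at r = 0
- at least one of the three: about 24-43%, against 12-14% at r = 0. With three independent tests one expects 1 − 0.95³ = 14%.

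The joint rates are lower because correlated predictors share the same signal and each is adjusted for the others.

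**Step 4: what these rates depend on.** They are set by r, the cut-off and n. The correlation between BIA and true nutritional status does not enter the calculation once r is fixed. That is a property of the set-up and not an empirical result, but it is the core of the point: the test does not examine that link.

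**The case against.** The strongest objection is that the circularity is inferred. Section 5 gives the data source for a prevalence aim, Section 8 leaves its malnutrition outcome undefined, and a case definition is commonly left to the statistical analysis plan. Section 3 also refers to other tests in the hospital records, and BMI is collected, so a non-BIA criterion is not excluded. This stands as a limit on certainty, and a reader who infers that the regression is certainly circular goes too far. It does not remove the point: the protocol states both the source of the classification and the predictors in focus, and a plan that follows both inherits the overlap.

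A reader might also take 74-94% as the false-finding rate of the planned analysis. The documents do not support this. That range is for one predictor tested alone at an assumed r of 0.7, while Section 8 plans a multivariable model, where the rates are much lower.

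A third inference would be that such a result says nothing about nutrition, so that every BIA predictor must be barred. That is also too strong. If the variable that defines malnutrition has some validity, agreement with another BIA output carries some information, though weak. Only variables used in the classification need to be kept out as predictors; the others can be reported for what they show.

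Finally, the damage is contained. The primary BIA-eGFR correlation, the clinical-outcomes part of the same sentence and non-BIA predictors are not touched.

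**Conclusion.** The point holds as a minor one. Read as written, the protocol puts BIA on both sides of a non-primary regression. The overlap is complete if the defining variable is also a predictor, and partial if different BIA outputs are used. The second case raises the chance of at least one significant BIA predictor in a three-predictor linear model from 12-14% to about 24-43%, and of a given one from 5% to about 8-16%. A single output tested alone spans about 16-94%. All of these rest on assumed correlations of 0.3-0.7 and an assumed prevalence of 20-40%; the protocol gives neither. The conclusion also rests on reading the Section 8 outcome as the Section 5 classification, which the protocol does not say expressly but for which it offers no alternative. The structural argument does not depend on the simulated figures.

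**What to change.** In Section 8, after the regression sentence, add text to this effect:

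- Any variable used to classify malnutrition or PEW, whether a BIA output or eGFR, is not entered as a predictor of it.
- Associations of the remaining BIA outputs with a BIA-based classification are reported descriptively, as agreement among BIA measures and not as predictors of malnutrition.
- If a nutritional reference independent of BIA and eGFR is already in the hospital records, it is named as the dependent variable, and BIA outputs may then be tested against it. Whether such a reference exists is an assumption; the protocol does not say.

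In Section 5, keep the prevalence aim and label the result as based on BIA and eGFR.

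The change is a few sentences, with no new measurement and no change to the primary objective. The real cost is scientific: without an independent reference on record, the claim that BIA predicts malnutrition is lost. What remains is a regression on factors such as dialysis duration and comorbidities with about 5-12 cases (assumed prevalence), which can only be exploratory. If an independent reference is used, a few more record fields must be extracted and some values may be missing.

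### Malnutrition is to be assessed from BIA (with eGFR) and then predicted from BIA measures, so those predictors can be significant by construction

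*Protocol*

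**What the plan says.** Section 5 makes the BIA-eGFR correlation the primary objective and adds a further aim: "The study will also assess the prevalence of malnutrition and protein-energy wasting (PEW) in the study population using BIA and eGFR data". The same section says that traditional kidney-function methods such as eGFR "provide an overview of kidney health but do not directly measure body composition or nutritional value". Section 4, on the other hand, describes BIA and eGFR as complementing each other in managing nutrition and hydration. Section 11 says of combined use: "Further studies are needed to validate combined assessment models and establish standardized protocols for their use in clinical practice".

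Section 8 lists the data: demographics with height, weight and BMI; five BIA measures (fat mass, fat-free mass, total body water, extracellular water, phase angle); and eGFR as the only item under laboratory parameters. It adds: "Clinical data such as dialysis duration and comorbidities will also be considered". On analysis it says: "Multivariate regression analysis will identify significant predictors of malnutrition and clinical outcomes, focusing on factors such as phase angle, lean body mass, and fluid status".

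Section 7 fixes the size: "Sample size: 25-30 adult hemodialysis patients will be recruited". Section 3 says that, apart from BIA, "All other reviewed tests are those that have already been performed for clinical reasons".

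**The concern.** Section 5 names the data from which malnutrition is to be judged, and Section 8 names the measures in which its predictors are to be sought. The two overlap. Phase angle and lean body mass are BIA outputs, and the only listed measures of fluid status are BIA's total body water and extracellular water. Section 8 lists no nutritional reference independent of BIA, such as serum proteins, dietary intake or a nutrition score. If a low BIA value is what makes a patient malnourished, finding that this value predicts malnutrition only restates the definition.

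A cut-off supplied in a statistical analysis plan would not cure this, because the protocol itself fixes both the source of the label and the focus of the predictors.

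eGFR raises a second, conditional concern. If it helps to classify patients, any later comparison of malnourished and other patients on eGFR is partly built in.

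At stake are the interpretation of a stated further aim and one regression outcome. A report could present phase angle or lean mass as significant predictors of malnutrition when the result would have appeared whatever the clinical truth.

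**Working it through.** The only stated figure is the sample size of 25-30. It comes without alpha, power or an expected prevalence, so there is nothing to reproduce. The check is therefore conditional.

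**Inputs.** From the documents: n = 25 to 30 (Section 7); label sources (Section 5); predictors in focus (Section 8). Assumed: 20-40% of patients labelled malnourished; two-sided alpha of 0.05; normally distributed measures; cut-offs and correlations as stated in each step.

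**1. Label is a cut-off on one BIA measure.** The k labelled patients are then exactly the k lowest on that measure, so the groups are fully separated. The exact two-sided rank-sum p-value is 2/C(n,k).

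| Cases | C(n,k) | p |
|---|---|---|
| 5/25 | 53,130 | 3.8e-5 |
| 8/25 | 1,081,575 | 1.8e-6 |
| 10/25 | 3,268,760 | 6.1e-7 |
| 6/30 | 593,775 | 3.4e-6 |
| 9/30 | 14,307,150 | 1.4e-7 |
| 12/30 | 86,493,225 | 2.3e-8 |

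The measure is significant in 100% of such studies.

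**2. Label is low on either of two BIA measures, A or B.** Each cut-off is the 16th or 20th percentile; 3,000 simulated studies per setting; Mann-Whitney test on A.

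| Correlation of A and B | A significant, n = 25 | A significant, n = 30 |
|---|---|---|
| 0 | 55-62% | 64-69% |
| 0.3 | 76-83% | 84-89% |
| 0.5 | 87-92% | 92-96% |

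An independent measure outside the label is significant in 4.0-5.2%. A fresh run with another seed agreed within about two percentage points.

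**3. eGFR in or out of the label.** Phase angle, fat-free mass, eGFR and true malnutrition are drawn independently, and the lowest 30% on an equally weighted sum are labelled; 4,000 runs.

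| Label | Phase angle significant (n = 25 / 30) | eGFR significant (n = 25 / 30) |
|---|---|---|
| Phase angle + fat-free mass + eGFR | 60% / 67% | 60% / 67% |
| Phase angle + fat-free mass | 84% / 89% | 4.5% / 4.2% |
| Independent of all three | 5.1% / 4.6% | 4.7% / 4.3% |

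Taking eGFR out removes the built-in eGFR association but leaves the BIA one. Both changes are needed.

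**4. Is dropping only the defining measure enough?** Label: lowest 30% on one measure. Tested: a second measure correlated with it at r. The second measure is significant in roughly 46-51% of studies at r = 0.5, 82-90% at r = 0.7 and over 99% at r = 0.9 (n = 25 to 30). Fat mass, fat-free mass and total body water come from one measurement and are mathematically linked, so a retained BIA measure can carry the same circularity.

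**5. What is left for a regression.** At 20-40% prevalence there are 5 (0.20 x 25) to 12 (0.40 x 30) cases. The smallest group difference in one outside predictor with 80% power (t-test) runs from 1.46 SD (5/25) to 1.08 SD (12/30). Exact 95% intervals for the prevalence are 31-40 points wide; for 9/30 the interval is 14.7-49.4%.

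**The case against.** The strongest reply concerns eGFR. Section 5 gives no case rule and nowhere says that a low eGFR makes a patient malnourished. Patients could be classified on BIA and then described by eGFR. A reader might infer that the protocol contradicts itself by classifying on a measure it calls unfit. The text does not support that: it says only that eGFR does not measure nutritional value directly, which leaves room for a supporting role, and Section 4 offers a rationale by calling the two complementary. The Section 11 remark on validation is a motive for the study, not an admission against it. This part of the reply stands. The eGFR point is a tension to clarify, not an error.

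A reader might also infer that the listed data cannot support the term PEW. The documents give no diagnostic criteria for PEW, so that claim would rest partly on outside standards. Section 3 also speaks of other reviewed tests in the plural, so the list may not be exhaustive. It is fair only to ask that the term be tied to a definition the data can support.

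Finally, the simulated percentages depend on invented labels, and it is true by definition that a cut-off variable separates the groups it creates. That is correct, but it is also the point: no choice of cut-off makes such a predictor informative. The predictors are introduced as examples, yet those named are the declared focus and are all BIA-based. Nothing in the protocol resolves the overlap.

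**Conclusion.** The concern holds as an overlap between label and predictors. To the extent that BIA defines malnutrition, the predictors in focus are expected to be significant by construction: about 55-100% of studies of 25-30 patients under the assumed labels, against about 5% for an unrelated outside measure. The exact percentages rest on the assumed prevalence, cut-offs and correlations; the direction does not.

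If eGFR also enters the label, the same applies to eGFR (60-67% under the equally weighted label in step 3). The protocol allows this reading but does not state it.

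Two further inferences are not supported. No size or direction of bias in the prevalence can be computed from the documents, and none is claimed; the wide intervals are sampling error at this sample size. Nor is the study's main result undermined: the primary BIA-eGFR correlation does not use the label, and the regression on clinical outcomes does not depend on it. The change should be made, but it concerns a further aim and one regression outcome.

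**What to change.** **Section 5.** State that eGFR describes or compares the groups and does not classify patients. Name the prevalence for what is measured: for example, the proportion with low values on one or more pre-chosen BIA measures, with cut-offs fixed before the data are seen and an exact 95% confidence interval. Keep the term PEW only with a stated case definition that the collected data, or values already in the hospital record, can support. Whether such values are available is an assumption.

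**Section 8.** Exclude from the malnutrition regression the BIA measures that define the label and any derived from or mathematically linked to them. Use predictors outside the label, such as age, dialysis duration and comorbidities. Keep them few and present the model as exploratory.

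**Cost.** About two sentences of wording and no new measurement; if PEW is kept, a few more values from records, some possibly missing. The aim becomes narrower. The remaining regression is weak, with about 5-12 cases at an assumed 20-40% prevalence, and can reliably detect only differences of about 1.1-1.5 SD.
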